
Procedures
	
The doctor explains what the study consists of and obtains informed consent. If the patient accepts, the FINDRISC will be verified, the inclusion and exclusion criteria are verified and the relevant data from their medical history will be recorded.
 
Subsequently, the subjects will be included in the study and randomized into two groups. In the participants of group A (intervention) they will be offered information on healthy lifestyles according to their result in the FINDRISC questionnaire and then a measurement of POC-A1c. In the participants of group B (control) they will be offered the same information on healthy lifestyles according to their FINDRISC result.
 
In addition, all randomized participants will be invited to perform a GPOT in the allied work of CAIMED or in the laboratory of their choice with the necessary preparation recommendations for the realization of the same. For this purpose, they will be given an order that includes the date of screening, a tracking number and time window in which they must go (i.e., 30 days and with a second attempt-maximum window at 90 days).
 
After 30 days from the delivery of the order for the PGTO, a call will be made to the randomized subjects to check if the exam was taken and its result requested in case it has done so, if the examination, you must send it to the center. Otherwise, the causes of not having made the previously recommended GTT will be investigated, and a new call will be made after 90 days. In patients who, if they attended the performance of the OGTT and obtained a presumptive result of diabetes (defined as an impaired oral glucose tolerance test and/or impaired POCA1C test according to the ADA guidelines), a closing call will be made 30 days after the test was done to confirm if they started to control their disease. For this, it will be instructed to attend consultation by general medicine according to what is contemplated by its entity administering benefit plans, ending the follow-up.
	

Analysis plan
	
For the primary objectives, the proportion of patients who attended the performance of the PGTT in each of the groups will be obtained and the statistical significance test for superiority in the follow-up ratio of the intervention group (A) over the control group (B) will be applied. Additionally, descriptive statistics will be obtained regarding the dynamics of application of the confirmatory test (i.e., latency time).
	

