A Pre-Screening activity will be carried out, with prior authorization of use of personal data, where the FINDRISC test will be applied to different population groups and in case the subjects obtain 12 points or more, they will be invited to participate in the study. Otherwise, participants with 11 points or less according to the application of FINDRISC will receive brief information on healthy lifestyles according to their risk group, ending the activity.

Once the Pre-Screening activity has been carried out, to carry out each day, a work site will be installed in the different places established to carry out the screening of the disease that will be attended by a doctor, bacteriologist, and nursing assistant. Subjects at risk identified by FINDRISC will be explained what the study consists of; if they wish to participate in it, and understand, accept, and sign the informed consent: the doctor will proceed to record the relevant data in their medical record, evaluate inclusion and exclusion criteria.

Subsequently, the participants will be randomized into 2 groups. Participants in group A (intervention) will be offered information on healthy lifestyles according to their outcome and will be given a measurement of POC-A1c*. In the participants of group B (control) they will be offered the same information on healthy lifestyles according to their FINDRISC result.

**The work site will have a properly covered cubicle, in which a POC-A1c equipment will be available with the necessary requirements of location and operation to guarantee the validity of the test. In this cubicle will be a laboratory assistant who executes the pre-analytical and post-analytical phase.*

In addition, all randomized participants will be invited to perform a GPOT in the CAIMED partner laboratory or in the laboratory of their choice with the preparation recommendations necessary for the realization of the same. For this purpose, they will be given an order that includes the date of screening, a tracking number and time window in which they must go (i.e., 30 days and with a second attempt-maximum window to 90 days).

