After 30 days from the application of the screening, a call will be made to the randomized subjects to check if they performed the indicated diagnostic test and the result of the OGTT, if the examination has been carried out, must be sent to the center (either by scanning, photographing, or bringing it to the research center). Otherwise, the causes of non-realization of the same will be investigated and a new call will be made after 90 days. In patients who, if they attended the performance of the OGTT and obtained a presumptive result of diabetes, a closing call will be made 30 days after the test was performed to confirm if they began control of their disease. For this, you will be instructed to attend a consultation by general medicine according to what is contemplated by your entity administering benefit plans, ending the follow-up.

Study population

Adult patients with no known diagnosis of diabetes attending a health care facility.

Inclusion criteria

- Adult, aged 18 years or older and under or equal to 75 years old
- Understand, accept, and sign informed consent
- FINDRISC greater than or equal to 12

Exclusion criteria

- Previous diagnosis of type 1 or type 2 diabetes mellitus
- Pregnancy or lactation at the time of inclusion in the study (referred by the subject)
- History of cancer in the subject (must be in remission for 5 years)
- Known history of familial hyperlipidemia
- Chronic use of systemic corticosteroids (Defined as: a dose greater than 5 mg of oral prednisolone or its equivalent and/or consumption greater than one month thereof).
- Known history of hemophilia or other bleeding disorders
- Known history of stage IV or V chronic kidney disease
- Known history of HIV
- Known history of sickle cell disease
- Known history of 6 phosphate dehydrogenase deficiency
- Known history of blood transfusion in the past 3 months
- Known history of erythropoietin therapy in the past 6 months.

Criteria and procedures for the withdrawal or suspension of subjects

Type and time of data collection corresponding to withdrawn subjects

The subject who decides to participate in the study can choose to withdraw at any time, since no therapeutic interventions are being applied, only guidance will be offered to the subject regarding their risk condition as has been established until that moment of the study and the moment in that its follow-up is terminated.

Whether to replace subjects and how

Withdrawn subjects will not be replaced.

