If the answer is I have not taken the test: Could you please tell us why you have not taken the sugar test? Wait for a response, and document it, end the call like this: "Remember that we will call you in 2 months again to confirm if the test was done."

**The answers are recorded by the platform and will be analyzed qualitatively by the researchers.*

Scheduling of study visits (schedule)

Responsible	Prescreening	Visit 1	Phone Call 1 (30 days ± 3 days)	Phone Call 2 (90 days ± 3 days)	Phone Call 3 (30 days after reporting to the center ± 3 days, if applicable)
Doctor Bacteriologist Research Assistant	– Conferences of application of FindRisc as risk screening				
Doctor		Explanation of the study, its procedures and obtaining the consent informed. Review of eligibility criteria.			
Research Assistant		VERIFICATION of FINDRISC, Randomization and data processing on the platform			
Research Assistant		Data processing on the platform to the corresponding group			
Laboratory		Implementation of POC-A1c			

Effectiveness comparison of the hemoglobin measurement glycosylated at the point of care (POC-A1c), vs the standard current based on tolerance test oral to glucose, for the detection early of Diabetes Mellitus guy 2 (DM2) in Colombia. **EDDIT-1 STUDY**

Version: 3.0
Date: February 15, 2022

CRS			Follow-up call 30 days after the PGT request.	Follow-up call - 30-90 days after admission to the study in patients not attending OGTT.	Verification call 30 days from the report of the result of the requested test. To those who present an impaired OGMP and have requested a control doctor.

Bias Control

- **Bias derived from the randomization process:** it is carried out through the Office - Excel platform by means of algorithms for the generation of random numbers and their assignment to the specific group, by means of a simple impaired randomization; in order to maintain the masking of the assignment, a number (1-2) will be assigned to classify the intervention and its comparator, keeping this hidden from most researchers.
- **Bias due to deviations from planned interventions:** from study design, with simple randomization, the subject who has received a group assignment cannot move on to the other.
- **Bias due to the lack of outcome data:** The number of stratified lost data of intervened versus non-intervened will be evaluated, if it exceeds 5% analysis and data imputation will be made.

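### A group A participant with a diabetes-range POC-A1c who never has the OGTT is given no written fallback referral, and no check that care started, in the available text

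*Combined protocol and SAP*

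**What the plan says.** The closing call is described in three places.

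- **Protocol Synopsis, Procedures.** The call is for OGTT attenders with a presumptive diabetes result: "In patients who, if they attended the performance of the OGTT and obtained a presumptive result of diabetes". A presumptive result is an impaired OGTT "and/or impaired POCA1C test according to the ADA guidelines". The call comes 30 days after the test, and the instruction to attend general medicine is attached to it.
- **Study procedures.** The attendance condition is the same, without the definition that mentions POC-A1c: "a closing call will be made 30 days after the test was performed to confirm if they began control of their disease".
- **Scheduling of study visits, Phone Call 3.** The clock is different: "Verification call 30 days from the report of the result of the requested test". The recipients are described as follows: "To those who present an impaired OGMP and have requested a control doctor".

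Non-attenders do receive something. Of all randomized participants, Study procedures says "they will be given an order that includes the date of screening, a tracking number and time window in which they must go". They are called at day 30 and, if still untested, again at day 90; the schedule describes that second call as "30-90 days after admission to the study in patients not attending OGTT". The screening site is "attended by a doctor, bacteriologist, and nursing assistant".

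In the call script under Instructions to the patient, advice to consult a doctor or health insurer appears only where the test was done. Where it was not, the caller asks why and announces another call in two months. The second call has no script of its own.

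**The concern.** POC-A1c is measured by the trial itself, in group A only. The Theoretical framework lists 6.5% or more as a diabetes criterion, and Annex 4 lets the final diagnosis variable rest on either the OGTT or POC-A1c. The trial could therefore hold a diabetes-range result, and even record diabetes, for someone whom its written call procedures never tell staff to refer. The plan itself expects four in ten of group A not to attend, so the situation is foreseeable.

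What is at stake is the care of a small number of participants. No estimate or test in the analysis plan depends on it.

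**Working it through.** **Reading the three descriptions together.** Take a group A participant with POC-A1c of 6.5% or more and no OGTT by day 90.

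| Source | Who gets the closing call | Clock starts at | This participant |
|---|---|---|---|
| Synopsis, Procedures | OGTT attenders with an impaired OGTT and/or POC-A1c | OGTT date | Not an attender; no date |
| Study procedures | OGTT attenders with a presumptive result | OGTT date | Not an attender; no date |
| Schedule, Phone Call 3 | Those with an impaired OGTT | Report of the result | No result; no report |
| Script, test done | Those tested: advised to consult if impaired | Not applicable | Wrong branch |
| Script, not done | Those untested: reason asked, next call announced | Not applicable | Applies; no advice to consult |

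The and/or wording in the Synopsis does not rescue the case. It defines a presumptive result inside the attendance condition, and the call is still timed from the OGTT.

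**Size.** Inputs from the Sample size section: 510 in group A and 60% expected attendance. The plan's own figures reproduce: 2 × 0.25 × (1.96 + 0.84)² / 0.10² = 392 per arm; 392 × 1.3 = 509.6, so 510; 510 + 392 = 902.

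Expected group A non-attenders: 510 × 0.40 = 204.

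The documents do not give the share with POC-A1c of 6.5% or more. Assume 2% to 15%. A high result may also prompt attendance, so attendance in this subgroup is taken as 60% (the planned group average), 80% or 90% (both assumed). Number concerned = 510 × share × (1 − attendance):

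| Share (assumed) | With such a result | 60% attend | 80% attend | 90% attend |
|---|---|---|---|---|
| 2% | 10.2 | 4.1 | 2.0 | 1.0 |
| 5% | 25.5 | 10.2 | 5.1 | 2.6 |
| 10% | 51.0 | 20.4 | 10.2 | 5.1 |
| 15% | 76.5 | 30.6 | 15.3 | 7.7 |

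The range is about 1 to 31 people.

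**Timing of a remedy.** The second call is allowed at 90 ± 3 days, that is days 87 to 93, while the OGTT window runs to day 90. Advice given on days 87 to 90 could still prompt a test that counts. On days 91 to 93 it cannot. Phone Call 3 at 30 ± 3 days after that falls between day 91 + 27 = 118 and day 93 + 33 = 126. Four months is about 122 days, and the Synopsis gives participation as approximately 4 months. Under the schedule, an attender who reports a result on day 93 could already be called as late as day 126.

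**The case against.** The strongest reply is that these participants are already directed to the right next step. The Theoretical framework requires two impaired tests for a definitive diagnosis, so after a single high POC-A1c the OGTT is what is needed. They hold an order for it and are called about it twice. This stands: a reader might infer that they are abandoned, and the documents do not support that. What remains is the missing fallback when the test is never done.

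A second reply is that this argues from silence while the likeliest places are out of sight. The Annex 1 flow figure and the consent form are not in the available text, and what the on-site doctor says at visit 1 is not described. This also stands, and it limits the conclusion to the available text. It does not remove the point, because the closing-call sections state a positive condition, attendance at the OGTT.

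Two other provisions might be thought to cover the case. The Synopsis says safety follow-up of the measurements and blood sampling will meet current standards, which is generic. The withdrawal section mentions guidance on the subject's risk condition, but names neither the POC-A1c result nor a referral.

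The schedule's words about a control doctor might be read as a further eligibility restriction. They look like poor translation and should not carry that weight.

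**Conclusion.** The point holds for the text that can be read: a group A participant with POC-A1c of 6.5% or more and no OGTT has no written fallback referral and no check that care started. It is a minor participant-care improvement. The size, about 1 to 31 of 510, rests on the assumed share and on the assumed attendance above 60%. The top of the range also requires attendance not to depend on the result, which sits uneasily with the trial's premise that POC-A1c improves attendance.

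A reader might go further and infer that the gap biases the comparison. It does not: the primary outcome is OGTT attendance, and the missing advice concerns people who have not attended. The differing clocks for Phone Call 3 (test date or result report) are a matter for clarification only.

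**What to change.** First check whether Annex 1, the consent form or the visit 1 counselling already covers this. If not:

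1. For group A non-attenders with POC-A1c of 6.5% or more, add advice to consult general medicine at the end of the existing second call, after OGTT attendance has been recorded. State the 6.5% cut-off explicitly, because Biochemical measurements calls any value of 5.7% or more impaired.
2. Extend Phone Call 3 to these participants about 30 days later, to ask whether care has started.
3. Make the second call on days 91 to 93 in both groups, so that the advice comes after the 90-day OGTT window has closed. Leave the day-30 script unchanged.
4. As a minor clarification, use one start date for Phone Call 3 in the Synopsis, Study procedures and the schedule.

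The cost is some rewording, one closing sentence, and about 1 to 31 extra calls by existing staff under the assumptions above. The second-call window shrinks from days 87 to 93 to days 91 to 93. The advice comes late, about three months after the result, which is the price of leaving the primary endpoint untouched.

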
Security monitoring and assessments
	
For the application of the FINDRISC screening questionnaire it is required to take non-invasive anthropometric measurements and to establish the status of prediabetes or undiagnosed diabetes, blood samples are required. The safety follow-up to these procedures will be carried out in accordance with current standards.
	

Title

Comparative effectiveness of point-of-care glycosylated hemoglobin measurement (POC-A1c), vs. the current standard based on oral glucose tolerance test, for the early detection of Type 2 Diabetes Mellitus (T2DM) in Colombia. **EDDIT-1 STUDY**

Theoretical framework

Type 2 diabetes mellitus (T2DM) is a growing public health problem in the world and in Colombia. In 2020, this pathology was considered the ninth cause of mortality in the world according to the global burden of disease (GBD) with more than 1 million deaths per year directly caused by diabetes (1). In Latin America, 1 in 3 adults living with diabetes are undiagnosed and in Colombia the behavior is similar, as reports from the High-Cost Account indicate that 3 out of every 100 Colombians have diabetes mellitus. However, the Ministry of Health and Social Protection estimates that the number is much higher and one in 10 people in Colombia suffers from this disease, this because at least half of the population does not know they have this pathology.

To reduce the gap of undiagnosed people, it is necessary to design and implement strategies for early detection of T2DM. The Berlin Declaration (2), published in October 2016 and supported by the IDF as well as other organizations, has identified early detection as a priority line and has set a goal for achieving this priority (2). This statement proposes to increase by 50% the number of people taking a risk test for T2DM and by 50% the number of high-risk people receiving a diagnostic test for T2DM.

According to this, it is important to consider the diagnostic criteria set forth by the American Diabetes Association (ADA) in 2022 (3):

- Fasting blood glucose (fasting - absence of caloric intake for at least 8 continuous hours) ≥ 126 mg/dL

or

- Oral Glucose Tolerance Test (according to WHO guidelines with an equivalent of 75 g of anhydrous glucose dissolved in water) at 2 hours: ≥ 200 mg/dL

or

- HBA1C $\geq 6.5\%$

or

- In patients with classic symptoms of hyperglycaemia or hyperglycaemia crisis, or random glycaemia ≥ 200 mg/dL

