*Note: To make the definitive diagnosis, it is necessary to perform two tests (the same or different) and that both are impaired.

Likewise, it defines as pre-diabetes, those patients who have impaired values of plasma glycemia as follows:

- Fasting plasma blood glucose: 100-125 mg/dL or

- Plasma glycaemia between 144-199 mg/dL 2 hours post OGTT

or

- HbA1c between 5.7% to 6.4%

In this way, and in accordance with the guidelines of the Colombian Clinical Practice Guidelines, an adequate and timely approach to the patient suffering from this disease avoiding serious long-term outcomes.

Background for the protocol

The risk score to predict the occurrence of DM2 was developed based on a prospective follow-up record conducted after a baseline survey from a census sample Finland's national of 4,450 subjects aged 34-74 years followed over 10 years. The validity,

	
Effectiveness comparison of the hemoglobin measurement glycosylated at the point of care (POC-A1c), vs the standard current based on tolerance test oral to glucose, for the detection early of Diabetes Mellitus guy 2 (DM2) in Colombia. EDDIT-1 STUDY
	
Version: 3.0 Date: February 15, 2022

---	--	---

specificity and predictive power of the risk score was initially assessed, both with cross-sectional data from the study and by comparing the scores with the results of the oral glucose tolerance study conducted on the same people. It was also validated with another population survey with a prospective five-year follow-up. The findings confirmed the high specificity and low false positive rate of the risk score for probability of development of DM2 (4).

As for the measurement of glycaemic levels, although a recent review by Barry et al. points out that screening with glycosylated hemoglobin (A1c) and basal glycaemia is imprecise (5), it is clear that in the Cases that are detected early, interventions can be made that prevent or delay the onset of diabetes and its complications. For their part, Barengo and Tuomilehto point out the importance of early detection of prediabetic patients with post-load glucose intolerance, to induce lifestyle changes that prevent the progression to diabetes (6).

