Follow-up of withdrawn subjects

Once the subject expresses his intention to withdraw, the follow-up will be terminated.

Criteria for the interruption of the study.

Since the intervention is not therapeutic and the technical conditions for performing laboratory tests are standardized, no a priori termination criteria are established.

Interventions

Description of interventions

The FINDRISC (applied in Pre-Screening activity) will be verified; for this it is necessary to take anthropometrics well as non-invasive measurements. Additionally, to establish the diagnosis of prediabetes or undiagnosed diabetes, invasive activities such as blood sampling are required.

Non-invasive measurements

Body weight (at 0.1 g precision) in lightweight underwear, without footwear, will be recorded at the screening visit as well as height (at 0.5 cm precision), that is, both measurements will be obtained at the beginning of the study. The waist and hip circumference will be taken twice, then the average of both measurements will be made.

Biochemical measurements

The PGTT will be carried out according to the standards of the allied laboratory or of preference by the patient, and under the local regulations of the country with the recommendations of the WHO. Ideally, the loading solution should contain 75 g of anhydride glucose and 1.6 g of citric acid, the first sample of glycemia will be obtained after 8 - 12 hours of fasting and the second sample will be obtained 2 hours after glucose loading. All this according to the recommendations described by the WHO.

PoC-A1c will be measured at the screening site using validated equipment that complies with international standards. Kits and processing methods will be ensured to be certified by the NGSP and standardized with the DCCT assay. The POC-A1c test shall be considered impaired for any value equal to or greater than 5.7% (3).

Enumeration of the participant

The enumeration of patients will be sequential since it is performed in a single center.

Allocation of the intervention

Once the participant has accepted and signed the informed consent, the doctor will verify the FINDRISC questionnaire previously applied in prescreening activities), as well as inclusion and exclusion criteria and random assignment will be carried out by the research team.

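### Presumptive diabetes has no stated cut-offs and can take in prediabetes, and the closing call has two start dates and two triggers

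*Combined protocol and SAP*

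**What the plan says.** **The label.** The Synopsis (Procedures) defines the group that gets the closing call (Phone Call 3) as OGTT attenders with a "presumptive result of diabetes (defined as an impaired oral glucose tolerance test and/or impaired POCA1C test according to the ADA guidelines". Study procedures uses the same term without defining it. Annex 4 (Final Diagnosis) has a Yes/No diabetes variable based on OGTT or POC-A1c under practice and ADA guidelines, also without a number.

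**The cut-offs.**
- Biochemical measurements: "The POC-A1c test shall be considered impaired for any value equal to or greater than 5.7% (3". The citation is to the ADA 2022 standards.
- Theoretical framework, diabetes: A1c of 6.5% or more, fasting glucose of 126 mg/dL or more, or an OGTT value "at 2 hours: ≥ 200 mg/dL".
- Theoretical framework, prediabetes: "HbA1c between 5.7% to 6.4" percent, or "Plasma glycaemia between 144-199 mg/dL 2 hours post OGTT".
- No section gives a number for an impaired OGTT.

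**The closing call.** Study procedures states that for those who attended and "obtained a presumptive result of diabetes, a closing call will be made 30 days after the test was performed". The Synopsis uses the same clock. In Scheduling of study visits, both the column heading and the cell count 30 days from the report of the result. The cell gives the call to those with an impaired OGTT who have asked for a doctor, and does not mention POC-A1c.

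**The concern.** The word *impaired* has to separate diabetes from prediabetes, and the protocol uses it for both. Staff who apply the study's own definition of an impaired POC-A1c would classify a participant with an A1c of 6.0% as presumptively diabetic. Staff who apply the diabetes criteria in the Theoretical framework would not. The same split arises for an OGTT value between the two printed levels.

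This bears on what participants are labelled, who gets the closing call, and possibly how the Annex 4 diabetes variable is filled in. Only group A has a POC-A1c, so the A1c route to a Yes exists in one arm only.

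The two clocks for the call are a separate matter. Participants may use a laboratory of their choice and must send the result in themselves. A clock that starts at the test can therefore expire before the centre knows that there is anything to follow up.

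**Working it through.** The plan gives no figure of its own on this point. The check compares the printed cut-offs and then works out the call dates.

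**1. A1c.** Three rules are applied to the same values.

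| POC-A1c | Impaired (Biochemical measurements, 5.7% or more) | Prediabetes (Theoretical framework, 5.7% to 6.4%) | Diabetes (Theoretical framework, 6.5% or more) |
|---|---|---|---|
| 5.6% | no | no | no |
| 5.7% | yes | yes | no |
| 6.0% | yes | yes | no |
| 6.4% | yes | yes | no |
| 6.5% | yes | no | yes |

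From 5.7% to 6.4%, impaired does not mean diabetes.

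**2. OGTT.** The note under the diabetes criteria says that for a definitive diagnosis "it is necessary to perform two tests (the same or different) and that both are impaired", which uses the word at the diabetes level. The next sentence describes prediabetes as "those patients who have impaired values of plasma glycemia as follows", which uses it at the lower level. A 2-hour value of 160 mg/dL falls in the printed 144-199 range, so it is or is not presumptive diabetes according to which use applies. This holds in both arms.

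**3. Trigger, one case.** Take a group A attender with A1c 6.0% and 2-hour glucose 130 mg/dL, and assume a fasting glucose below 100 mg/dL.
- Synopsis with the Biochemical measurements definition: presumptive diabetes, closing call.
- Synopsis with the 6.5% reading: not presumptive diabetes, no closing call.
- Visit schedule: the OGTT is not impaired, so no closing call.

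**4. Clock.** Let T be the day of the test and R the day of the report, both counted from inclusion. The two due dates are T + 30 and R + 30, so they differ by (R + 30) − (T + 30) = R − T. The documents give no reporting delay. The table assumes that, apart from the same-day case, the result is first reported at Call 1 (day 30) or Call 2 (day 90).

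| T | R | Due, test clock | Due, report clock | Difference |
|---|---|---|---|---|
| any day | same day | T + 30 | T + 30 | 0 days |
| 1 | 30 | 31 | 60 | 29 days |
| 31 | 90 | 61 | 120 | 59 days |
| 60 | 90 | 90 | 120 | 30 days |
| 90 | 90 | 120 | 120 | 0 days |

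The test-based call falls due before the report when T + 30 < R. For a test after Call 1 that is first reported on day 90, this means T < 60, so tests on days 31 to 59. If the schedule's 3-day tolerance is added, T + 33 < 90 gives days 31 to 56.

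**5. Reach.** Setting the primary endpoint defines the outcome as the probability of going to the OGTT, whatever its result. The sample size uses 60% against 50% attendance. Neither uses the presumptive label or Call 3. The telephone script in Instructions to the patient concerns the OGTT only, so it shares the OGTT ambiguity in step 2 but not the A1c one.

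**The case against.** The best defence is that the Synopsis refers to diabetes *according to the ADA guidelines*, that the Theoretical framework prints those criteria, and that its note on definitive diagnosis uses *impaired* at the diabetes level. On that reading 6.5% and 200 mg/dL were meant throughout. This is a natural reading, so a reader who infers that the protocol definitely classes prediabetes as diabetes goes too far. It does not close the matter, because Biochemical measurements cites the same ADA reference for 5.7% and is the only place where an impaired POC-A1c is defined.

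A reader might also infer that the visit schedule deliberately limits the call to people who have already sought a doctor. The wording says so, but the English is uneven, and the phrase may be a garbled form of the instruction to attend general medicine. It should be clarified rather than treated as a settled second criterion. The absence of POC-A1c from the schedule does not depend on that phrase, although the A1c route itself is spelled out only in the Synopsis.

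The 29-day and 59-day differences should not be read as expected delays. Participants may send results promptly, and a same-day report gives no difference. That the clocks differ stands; the size is illustrative.

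Finally, it can be said that little depends on this, since no planned analysis compares diabetes counts between arms. That stands, and it limits the weight of the point.

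**Conclusion.** The point holds as an inconsistency in definitions and timing. Taken with the study's own definition of impaired, the Synopsis can label an A1c of 5.7% to 6.4% presumptive diabetes. An impaired OGTT has no stated cut-off. Call 3 has two clocks and, as worded, two triggers.

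The consequences are limited to how participants are labelled, who receives Call 3 and when, and possibly the Annex 4 diabetes variable. A reader might infer that the arm comparison is biased; the documents do not support that, because the primary endpoint is attendance and its test and sample size do not use the label.

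The number of participants affected cannot be derived from the documents. The timing gap equals the delay from test to report. The day ranges in which the call falls due too early rest on the assumption that the result is first reported on day 90. The trigger case rests on an assumed normal fasting value.

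**What to change.** - **Presumptive diabetes.** Define it by the thresholds already printed in the Theoretical framework: A1c of 6.5% or more, or 2-hour OGTT of 200 mg/dL or more. Add fasting glucose of 126 mg/dL or more if that value is recorded. Put the definition in Study procedures as well as the Synopsis.
- **The 5.7% cut-off.** Keep it, under a different word such as *altered*, for the conditional probability in Description of statistical methods, where it is appropriate.
- **Call 3.** Use one trigger (presumptive diabetes as defined, whether or not a doctor was requested) and one clock (30 days from the report) in the Synopsis, Study procedures and the visit schedule.
- **Annex 4 diabetes variable.** Apply the same rule and state that the result is presumptive, since the protocol asks for two tests for a definitive diagnosis. If counts are ever shown by arm, use the OGTT criterion alone, because group B has no POC-A1c.

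The cost is protocol wording and one derived-variable rule. A fasting criterion needs one more data field: Biochemical measurements already takes a fasting and a 2-hour sample, but Annex 4 lists a single OGTT result. For a result reported at Call 2, the report clock ends at day 90 + 30 = 120, or 93 + 33 = 126 with both 3-day windows, which fits the roughly four months of participation in the Synopsis. The primary analysis and sample size do not change.
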